## 2.0 Objectives

Aims: In collaboration with three subject recruitment venues (SRVs) in the Adolescent Medicine Trials Network or HIV/AIDS Interventions (ATN), *Scale It Up (SIU)*, our goals are to better understand HIV-prevention focused self-management behaviors among HIV-negative YMSM, and to study the implementation of YMHP to improve the portability and scalability. Our CET design gathers information about implementation. In a “Hybrid 2” trial, the dual goals are to determine which treatments work in which settings and to simultaneously answer implementation science questions about the potential barriers/facilitators to a treatment’s widespread and sustained implementation. The SRVs will help the study assess and address practical problems at the frontline of service provision to pave the way for a comprehensive program to reduce HIV infection among YMSM that reflects the complexities of real-world adolescent HIV clinics.

Aim 1: Adapt YMHP for clinic and remote delivery (via phone or video chat) by existing HIV clinic staff, CHWs, who work with YMSM aged 15-24. We will consult with staff to obtain input on how best to implement YMHP to maximize feasibility, acceptability, and sustainability. This input will also identify issues with adapting YMHP for delivery for YMSM aged 15-18, and for remote delivery.

Aim 2: Assess the effectiveness of YMHP when delivered in a real world setting compared to a treatment as usual control – individual HIV testing – which represents a common standard of care.

Aim 2a: Assess the cost effectiveness of both delivery formats of YMHP to enhance the likelihood of uptake of this best evidence intervention.

Aim 2b: Assess the five components of the self-management model and how these components vary over time, are directly improved by the interventions, and mediate intervention effects.

Aim 3: Test a sustainable model of YMHP implementation in real world adolescent clinics. We will utilize local supervisors within the clinic setting to sustain the CHWs fidelity to delivering the MI-based YMHP intervention. We will monitor fidelity throughout the trial and conduct assessments and qualitative interviews with key stakeholders to determine the barriers and facilitators of YMHP implementation utilizing the *SIU Exploration, Preparation, Implementation, Sustainment (EPIS)* model (see ATN 153 EPIS Study Procedure Guide).

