1.2 Quantitative Analysis Plan

The primary hypothesis is that receipt of YMHP (regardless of delivery format) will be associated with greater improvements in sexual health management (as measured by decreased STIs, CAS and increased PrEP uptake/adherence) as well as greater reductions in substance use, compared with youth who receive the standard of care (individual HIV testing) only. Our secondary hypothesis is that youth who elect to receive YMHP remotely will report more barriers to accessing health care compared to those who elect to receive the intervention in clinic. In addition, we hypothesize that remote-based YMHP will demonstrate greater improvements in sexual health management (as measured by decreased STIs, CAS, and increased PrEP uptake/adherence) as well as reductions in substance use, compared to clinic-based YMHP, among YMSM who do report barriers to health care access. In contrast, it is hypothesized that clinic-based YMHP will demonstrate greater improvements in sexual health management and reduced substance use among YMSM who do not report barriers to health care access. Self-management model analysis is described in the AC.

The AC will test the effect of clinic-based versus remote delivery on STI rates, alcohol and drug use behavior, CAS, and PrEP uptake through multi-level growth mixture modeling (GMM). A separate model will be run for each outcome. Each model will be a 2-level model in which individuals (Level I) are nested in clinics (Level II). This approach controls for the non-independence of individuals within clinics. Because three SRVs provide extremely limited predictive power at Level II, no site covariates are included in the model. (The models are empty at Level II).

In a GMM, a latent growth curve with an intercept and linear slope factor is specified. Latent class analysis is applied to these 2 growth components (intercept and slope) to identify groups of individuals who share trajectories. For example, with regard to drug or alcohol use, “immediate and sustained responders” may have the lowest post-intervention intercept and a flat slope. Meanwhile, “non-responders” might have the highest post-intervention intercept and a flat slope. In contrast, “delayed responders” might have a high post-intervention intercept but a significant negative slope, indicating reductions in missed medication over the follow up period.

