If modeling results indicate that discrete classes are not present, we will proceed with analyses in which the growth factors (intercept and slope) are predicted directly by intervention condition (and demographic factors found to be associated with condition after randomization or with attrition over follow up). GMMs can subsequently incorporate predictors of class membership. These analyses can be conceptualized as a multi-nominal logistic regression with the latent trajectory-class membership constituting the outcome. The predictors

of primary interest will be intervention condition, the presence of any barriers to health care access, and the interaction between condition and barriers to access. We will include as covariates any demographic variables that were associated with condition after randomization or with attrition over the follow up period.

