1.2.1 Power Analysis

First, we analyzed power assuming independence of participant observations (assuming that the nesting of people-within-clinic was irrelevant). With regard to STIs, we utilized the “repeated measures” module of PASS 13.0 to examine power to detect odds ratio differences in a repeated measures design. Specifying compound symmetry, we allowed ρ to vary between .2 and .5. Assuming the prevalence of STIs in the remote-based condition varies between .05 and .15, the proposed design ($N = 270$) has power .80 to detect an odds ratio of .20 to .50. Similarly, with regard to the odds of PrEP uptake, allowing the rate of uptake in the remote-based condition to vary between .05 and .20 and allowing ρ to vary between .4 and .7, the proposed design has power of .80 to detect an odds ratio of 1.9 to 2.3. With regard to number of alcohol and drug use days, we utilized the *Tests for Two Poisson Means* module in PASS 13.0. Based data from our previous studies, we allowed the rate of heavy drinking in the phone-based condition to vary between 7 and 9 days during a 30-day assessment. The study is adequately powered to detect a 3% reduction in number of heavy drinking days in the clinic-based condition at any single follow up point. Allowing the rate of drug use in the remote-based condition to vary between 3 and 5 days during a 30 day assessment period, the study is adequately powered to detect a 4% reduction in drug use in the clinic-based condition. A similar analysis was conducted with respect to CAS. Based on our previous research, we allowed the rate of CAS in the phone-based condition to vary between 2 and 4 acts in a 30 day assessment period. The study is powered to detect a difference as small as 5% between the remote and clinic-based YMHP conditions. The nesting of individuals within SRVs has the potential to reduce power because substantial variability in outcome across SRVs can obscure level II treatment effects [70, 71]. The design effect can be used to tailor power analyses calculated under assumptions of independence. In the case of a Level I predictor with a fixed effect which is uncorrelated with other covariates in the model, the design effect is equal to the $1 - \rho$, where ρ is the intra-class correlation or the percentage of variance accounted for by variability between SRVs [71]. In previous intervention trials conducted within the ATN [72], between clinic site variability in HIV related outcomes did not differ significantly from zero. Based on the characteristics of ATN clinics, we anticipate a similar absence of variability across clinics, suggesting that the design effect would result in a negligible reduction in power. Finally, a sample size of 270 is sufficient to detect a moderation effect with an f^2 of .02. Cohen [73] designates this as a small effect, however recent work has characterized an effect of this size as moderate to large as applied to moderation [74].

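### The SAP's outcome models and power section are written for clinic-based versus remote delivery, not for the randomised YMHP versus standard-of-care comparison in its own primary hypothesis

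*SAP*

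**What the plan says.** SAP 1.2 opens with "The primary hypothesis is that receipt of YMHP (regardless of delivery format" and makes standard-of-care HIV testing the comparator. Protocol 2.0, Aim 2, agrees: "Assess the effectiveness of YMHP when delivered in a real world setting compared to a treatment as usual control".

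The next paragraph of SAP 1.2 introduces the growth mixture models, one per outcome: "The AC will test the effect of clinic-based versus remote delivery on STI rates, alcohol and drug use behavior, CAS, and PrEP uptake". Further on, the predictors of latent class membership "of primary interest will be intervention condition, the presence of any barriers to health care access", together with the interaction of the two. If no classes emerge, intervention condition predicts the intercept and slope directly. The SAP does not list the levels of that variable.

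SAP 1.2.1 gives power for five outcomes:
- STIs: "Assuming the prevalence of STIs in the remote-based condition varies between .05 and .15". PrEP uptake is handled in the same way.
- Heavy drinking: "we allowed the rate of heavy drinking in the phone-based condition to vary between 7 and 9 days", against a reduction in the clinic-based group.
- Drug use: "the study is adequately powered to detect a 4% reduction in drug use in the clinic-based condition".
- CAS: "The study is powered to detect a difference as small as 5% between the remote and clinic-based YMHP conditions".

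**The concern.** The hypothesis and the model sentence describe different comparisons. The first is between randomised arms. The second, under the current scheme, is between groups that chose their own format, and it has no place for a participant assigned to HIV testing only. An analyst who follows the model sentence would not test Aim 2. An analyst who follows the hypothesis would. Both could claim to have kept to the plan, and the choice could be made after the data are seen.

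The power section raises the same problem at the design stage: a reader cannot learn from it what YMHP effect against standard of care the trial can detect.

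**Working it through.** **1. Which comparison each place describes.**

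| Place | Comparison |
|---|---|
| SAP 1.2, hypothesis | YMHP (either format) vs standard of care |
| Protocol 2.0, Aim 2 and Hypothesis | same |
| Protocol 4.0 | both formats, over standard of care |
| Protocol 6.0, Randomization | two randomised conditions: YMHP and HIV testing |
| Protocol 1.0, intervention row, from 10/15/19 | YMHP with chosen format vs standard of care |
| Protocol 1.0, Primary Objective row | clinic-based vs remote |
| SAP 1.2, model sentence | clinic-based vs remote |
| Protocol 5.0, and 6.0 on YMHP sessions | format described as randomised |

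**2. Who can enter a clinic-versus-remote model.** Protocol 6.0 offers YMHP to the HIV-testing arm only from the 9-month follow-up visit, so that arm has no format while outcomes accrue. In the YMHP arm, format is the participant's choice (Protocol 2.0, Phase 2) and may change between sessions (Protocol 6.0). Before the COVID changes the first session was in person for everyone. Only the earlier subsample in the Secondary Aim (Protocol 2.0) was randomised to format; its size is not given.

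If *T* is the total and *k* the unstated number earlier randomised to format, the control arm left out is (*T* − *k*)/2 at an assumed 1:1 allocation. That is at most 135 of 270 or 90 of 180. At an assumed 2:1 it is at most 90 or 60. The documents give no allocation ratio.

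**3. What intervention condition means.** For randomised arm: Protocol 6.0 uses the term for YMHP and HIV testing, and SAP 1.2, 1.2.2 and 1.2.3 tie condition to randomisation. For format: Protocol 5.0 and SAP 1.2.1 use condition for in-person, remote, phone and clinic delivery, and SAP 1.2 crosses it with barriers to access, which is the structure of the secondary hypothesis on format. The text does not settle it.

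**4. Tally of the power statements in SAP 1.2.1.**

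| Outcome | Reference rate | Group | Comparator |
|---|---|---|---|
| STI | .05–.15 | remote | not named |
| PrEP uptake | .05–.20 | remote | not named |
| Heavy drinking | 7–9 days | phone | clinic |
| Drug use | 3–5 days | remote | clinic |
| CAS | 2–4 acts | phone | clinic |

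Standard-of-care reference rates: 0 of 5. Explicit remote or phone versus clinic: 3 of 5. No comparator named: 2 of 5. The separate moderation statement (f² of .02) names no contrast.

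**5. Can the figures simply be relabelled?** I tried to reproduce the count figures, assuming two-sided 5%, 135 per group, pure Poisson counts and no dropout. Power is Φ(λδ/√(λ(2 − δ)/n) − 1.96). For heavy drinking with λ = 7, δ = .03, n = 135: difference 0.21, standard error √(13.79/135) = 0.320, ratio 0.66, power Φ(−1.30) = about 10%. Over the stated ranges, power is 10–11% for the 3% drinking reduction, 8–11% for 4% drug use and 9–13% for 5% CAS. The plan's figures are therefore not reproduced under these assumptions. That is a separate matter, since the SAP states neither alpha nor allocation, but it means they cannot be carried over to another contrast.

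For illustration only, with the SAP's remote and phone rates standing in for the missing standard-of-care rates, the same approximation at 80% power and 135 per arm gives detectable reductions of 11.0–12.5% (drinking), 14.7–18.7% (drug use) and 16.3–22.7% (CAS). The gap from 3–5% comes from the failure to reproduce, not from the change of contrast: with equal rates and group sizes, a two-group calculation does not depend on the labels. What the contrast changes is which rates and how many participants belong in it.

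**The case against.** The strongest reply is that the plan already contains the right analysis. The hypothesis comes first, the Secondary Aim in Protocol 2.0 places format among secondary questions, and intervention condition, read with Protocol 6.0 and the SAP's own references to randomisation, covers both randomised arms. This stands in part. A reader might infer that the SAP discards the control arm or never tests the primary hypothesis. The documents do not support that: the omission follows from one sentence, and the later predictor can be read to include standard of care. What remains is that the levels are undefined and the only contrast spelled out for the models is a different one.

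A second reply is that clinic-versus-remote is a stated objective, since the Primary Objective row of Protocol 1.0 names it. That is true, and the SAP sentence is therefore not a stray slip. But the same table records the change from 10/15/19 to YMHP versus standard of care, and the hypothesis in both documents follows the change. The row is one more passage to reconcile, not a reason to keep the model sentence.

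Third, format is a legitimate question, and part of the sample was randomised to it. That also stands, as a secondary analysis.

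**Conclusion.** The point holds as a mismatch between the primary hypothesis and the sentence and power calculations meant to serve it, together with an undefined key predictor. It should be settled before any outcome analysis, because it decides which arms are compared. Its size is best given by the tally: none of the five outcome power statements uses a standard-of-care rate. This rests on the text alone. The control-arm counts depend on an assumed allocation and are upper limits.

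A reader might also infer that the trial is underpowered for YMHP versus standard of care. The documents do not show that: power for this contrast is unstated, and without standard-of-care rates, the allocation ratio and the number randomised under the current scheme it cannot be computed. The conflict over total sample size (270 in Protocol 2.0, Protocol 12.0 and SAP 1.2.1; 180 in Protocol 1.0, and 60 at each of three sites in Protocol 25.0) would exist whichever contrast were primary. It is a separate issue and adds no weight here.

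**What to change.** - **SAP 1.2.** Replace the clinic-versus-remote sentence. Define the primary predictor, and intervention condition wherever it appears, as randomised arm: YMHP in either format versus standard-of-care HIV testing, analysed as randomised.
- **Earlier participants.** State whether those randomised to format enter that model. As described, they have no concurrent randomised standard-of-care comparator, so the default is to leave them out of the randomised contrast.
- **Format.** Make clinic versus remote a secondary analysis that separates participants randomised to format from those who chose it, and say how someone with sessions in both formats is classified.
- **SAP 1.2.1.** Restate power for YMHP versus standard of care, with assumed standard-of-care rates, the allocation ratio, the number randomised under that scheme and one reconciled total.
- **Protocol.** Reconcile the Primary Objective row in 1.0, and the statements in 5.0 and 6.0 that format is randomised, with the 10/15/19 sentence in 1.0, the Phase 2 description in 2.0 and the Randomization text in 6.0.

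The cost is SAP and protocol wording and a re-run of the power calculations. No study procedure changes. The detectable effects may become less favourable, and whether the number randomised is enough cannot be judged until they are restated.

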Secondary Aim: The design will result in a subsample of youth who were randomized to receive YMHP in a clinic-based or remote delivery. It will also yield a subsample who are allowed to self-select delivery method. We will utilize these subsamples to assess youth preferences for

PROTOCOL TITLE: Comparative effectiveness trial of clinic-based delivery of an HIV risk reduction intervention (YMHP) for YMSM, Phase 2

delivery format, evaluate whether delivery format is associated with session retention, and test for any indications that delivery format is associated with response to intervention.

We will achieve our aims over 2 phases of the study.

Phase 1: We conducted focus groups with youth as part of our formative research to obtain implementation feedback about the delivery of the YMHP intervention and intervention components to ensure culturally competent, feasible, and scalable implementation both in the clinic setting and via remote delivery. Feedback from these focus groups at the 3 SRVs has been used to modify the YMHP intervention prior to the launch of Phase 1. Phase 1 focus groups were conducted with youth at each of the 3 SRVs to gather information that would be used to better implement YMHP. Groups were broken down into two age groups, 15-17 and 18-24.

We will train a minimum of 2 CHWs at each SRV to deliver the YMHP sessions, who must demonstrate competence according to the Motivational Interviewing Treatment Integrity (MITI) before providing the intervention in Phase 2.

Phase 2: We will recruit and enroll 270 YMSM, aged 15-24, 90 at each of the 3 SRVs. Enrollment will be limited to HIV-negative YMSM who report recent substance use and either CAS or a positive STI test result. Participants will be randomized to receive a standard of care enhanced HIV testing and counseling versus the YMHP intervention in person or by remote delivery (initial in-person session). The modality of delivery is chosen by the participant and involves completion of the 4 YMHP sessions and the delivery of pre-exposure prophylaxis (PrEP) information and navigation services to interested participants. Fidelity will be monitored throughout the trial. Sessions will be audio-recorded for MITI fidelity coding, and CHWs and supervisors will be given implementation support throughout the study period.

The current application is for Phase 2; Phase 1 has already been complete.

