## **5.0 Study Intervention**

### **Intervention Design and Procedures**

YMHP is a CDC Best Evidence Intervention that utilizes motivational interviewing (MI) to reduce CAS and substance use among YMSM. The YMHP intervention will be delivered by MI-trained CHWs employed at clinics, primarily by former HIV C&T counselors, health educators, and trained program peers. Participants will be randomized to receive the intervention either in person or remotely. Both conditions involve completion of the 4 YMHP sessions and the delivery of PrEP information and navigation services to interested participants.

YMHP is a CDC Best Evidence Intervention that utilizes motivational interviewing (MI) to

**PROTOCOL TITLE:** Comparative effectiveness trial of clinic-based delivery of an HIV risk reduction intervention (YMHP) for YMSM, Phase 2

reduce CAS and substance use among YMSM. The YMHP intervention will be delivered by MI-trained CHWs employed at clinics, primarily by former HIV C&T counselors, health educators, and trained program peers. Participants will be randomized to receive the intervention either in person or remotely. Both conditions involve completion of the 4 YMHP sessions and the delivery of PrEP information and navigation services to interested participants.

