**Assurance of Intervention Fidelity**

All sessions (remote and clinic-based) will be audio-recorded and sent for MITI coding. For the pre-trial phase, both CHWs and supervisors will mock the intervention and submit 4 roleplays of

**PROTOCOL TITLE:** Comparative effectiveness trial of clinic-based delivery of an HIV risk reduction intervention (YMHP) for YMSM, Phase 2

intervention in-person and 4 roleplays of the intervention remotely delivered. Then supervisors will complete one session of supervision with each CHW and audio recordings will be uploaded onto the site Dropbox Business account.

Mocks will be coded using MITI thresholds for fidelity flagging. Those 5 criteria are: percent reflection, percent complex reflection, technical global, relational global and MI non-adherent (MINA) codes. For clearance, trainees should be scoring in the “fair range” on all 5 elements by their final mock. If they are below in one or two areas, they don’t have to redo the mock. However, by the mock of Session 4 they should be at least “fair” in all elements to be cleared.

For ongoing monitoring, MITI coding randomizer should flag for additional review any session where the CHW falls below fair on more than 2 of those domains. One recording per CHW will be randomly selected for MITI coding by the study team on a regular basis. All the randomly coded sessions, not just the flagged MITI forms, will be shared with the supervisors for them to trust their barometers for “good enough” MI instead of only having MITI to compare when things were “bad.”

For the full-trial, each CHW will complete and submit an electronic Clinical Session Form via Qualtrics upon completion of each YMHP session.

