HIV testing is a prevention service already provided by the staff at each SRV as part of their existing outreach and testing services (which are funded and monitored by local health department and CDC contracts). Everyone who is enrolled into the study will have had HIV testing as part of the screening process prior to study enrollment. If a participant is randomized to standard of care HIV testing, they will not attend any further sessions. The study staff will ensure that the participant has received referrals to available services, including PrEP services. They will be scheduled for their immediate post-test assessment 3 months after BL. They will also be given the option to complete the 4 YMHP Sessions after the 9month follow-up (12month follow-up post BL).

*Immediate Post-test Assessment (3 months after BL)*

After completing YMHP sessions, participants will be scheduled to complete an immediate post-test assessment (IP). This assessment will occur about three months after their baseline assessment (i.e., the first follow-up assessment post-baseline). During this assessment participants will complete a CASI about their drug use, sexual behavior and general thoughts and feelings. In addition to assessing the primary outcomes of the intervention, participants will also respond to process measures. Specifically, participants will be asked to provide an evaluation of their counselor, as well as the health care climate of the YMHP intervention. This CASI can be completed at the SRV or remotely. Participants access the CASI through a survey link sent directly to their email, and takes approximately 45 minutes to complete.

During this visit (or anytime after the Intervention window closes, which is 3 months after Baseline) a participant may be asked to participate in an optional qualitative feedback interview. Participants will be called by a research staff member at PRIDE or at one of the other sites to complete a 30 minute interview over the phone. This interview will be offered in the immediate post test assessment, but can be completed at any time 3 month after the BL.

*Immediate post-test assessment*

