## **25.0 Multi-Site Research**

This research is being conducted at Wayne State University Prevention (W'SUP) at Wayne State University in Detroit, MI, the University of Miami Division of Adolescent Medicine in Miami, FL, and the Children's Hospital of Philadelphia (CHOP) Division of Adolescent Medicine in Philadelphia, PA.

Each site will enroll 60 individuals.

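### The SAP clusters by clinic only and ignores the CHWs who deliver YMHP; a prespecified sensitivity analysis with a CHW effect in the YMHP arm should be added

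*SAP*

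**What the plan says.** **Delivery.** Protocol 5.0 (Intervention Design and Procedures) states: "The YMHP intervention will be delivered by MI-trained CHWs employed at clinics". Protocol 2.0 sets the number: "We will train a minimum of 2 CHWs at each SRV to deliver the YMHP sessions". With three sites that is at least six CHWs. No maximum is given, and 5.0 provides for training replacements. Protocol 6.0 describes four sessions of roughly 40 to 60 minutes.

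**Control arm.** Protocol 6.0 (HIV testing condition) states: "If a participant is randomized to standard of care HIV testing, they will not attend any further sessions". Under Randomization in the same section, a CHW does meet each control participant to cover risk assessment and referrals, including PrEP. YMHP is offered to controls only after the 9-month follow-up.

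**Analysis.** SAP 1.2 states: "Each model will be a 2-level model in which individuals (Level I) are nested in clinics (Level II"), and leaves the clinic level without covariates. SAP 1.2.1 discusses only variability between sites and concludes that there is little to worry about, "suggesting that the design effect would result in a negligible reduction in power". CHW does not appear in the SAP as a level, random effect, covariate or sensitivity analysis.

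**CHW data.** Protocol 5.0 (Assurance of Intervention Fidelity) states that "each CHW will complete and submit an electronic Clinical Session Form via Qualtrics upon completion of each YMHP session".

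**Sample size.** Protocol 2.0 says "We will recruit and enroll 270 YMSM, aged 15-24, 90 at each of the 3 SRVs", while 25.0 says "Each site will enroll 60 individuals", which makes 180. Both are used below.

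**The concern.** Participants treated by the same CHW may have correlated outcomes. Here that correlation would sit mainly in one arm, because only YMHP participants receive the counselling sessions. This is a partially nested design.

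A clinic effect is common to both arms and drops out of the treatment contrast. A CHW's particular skill at delivering YMHP does not: it moves that CHW's YMHP participants and leaves the controls in the same clinic where they were. With few CHWs, such differences do not average out, and a model that knows only clinics treats the YMHP participants within a clinic as independent.

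The design-effect argument in SAP 1.2.1 does not reach this. Its factor, one minus the between-site correlation, is never above 1 and describes variation shared by both arms. Clustering by CHW in one arm inflates the variance instead. The evidence cited there is also about clinics, not about the people delivering the intervention.

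At stake is the precision claimed for the primary hypothesis. An apparent YMHP effect could partly reflect which few CHWs delivered it, in a trial whose aims include portability and scalability.

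**Working it through.** **The plan's own figure.** SAP 1.2.1 gives no numerical ICC for clinics and none for CHWs, so there is no design effect to reproduce. Its power of .80 at N = 270 for an STI odds ratio of .20 to .50 compares remote with clinic-based delivery, under independence. Alpha, sidedness, number of repeated measurements and allocation are not stated. With 135 per arm and a two-sided .05 test, approximations come near .80 only at a repeated-measures correlation of .2. The figure is neither confirmed nor refuted, and it does not bear on CHWs.

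**Inputs.**
- N = 270 or 180 (Protocol 2.0 and 25.0).
- CHWs: 6 (the Protocol 2.0 minimum); 12 is an assumed alternative.
- Allocation 1:1: assumed, as no ratio is stated.
- CHW ICC .01 to .10: assumed, as none is given.
- Continuous outcome and a clinic-adjusted linear model: a simplification.

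**Formulas.** YMHP participants per CHW: m = (N/2) / number of CHWs. YMHP-arm design effect: DE = 1 + (m − 1) × ICC. Control-arm design effect: 1. At 1:1, true variance / model variance = (DE + 1)/2, and the SE ratio r is its square root. The actual two-sided type I error of a nominal .05 test is 2 × [1 − Φ(1.96/r)].

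**Worked case.** N = 270, 6 CHWs, ICC .05: m = 135/6 = 22.5; DE = 1 + 21.5 × .05 = 2.075; (2.075 + 1)/2 = 1.5375; r = 1.24; 1.96/1.24 = 1.58; type I error 11.4%.

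| N | CHWs | m | | ICC .01 | .02 | .05 | .10 |
|---|---|---|---|---|---|---|---|
| 270 | 6 | 22.5 | SE ratio | 1.05 | 1.10 | 1.24 | 1.44 |
| | | | Type I error | 6.3% | 7.5% | 11.4% | 17.4% |
| 270 | 12 | 11.25 | SE ratio | 1.03 | 1.05 | 1.12 | 1.23 |
| | | | Type I error | 5.6% | 6.2% | 8.0% | 11.1% |
| 180 | 6 | 15 | SE ratio | 1.03 | 1.07 | 1.16 | 1.30 |
| | | | Type I error | 5.8% | 6.6% | 9.2% | 13.3% |
| 180 | 12 | 7.5 | SE ratio | 1.02 | 1.03 | 1.08 | 1.15 |
| | | | Type I error | 5.4% | 5.8% | 6.9% | 8.9% |

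**Simulation check.** Simulated trials with three clinics, clinic adjustment and CHW effects in the YMHP arm only (N = 270, 6 CHWs) gave type I error of 5% at ICC 0, 6–7% at .01, about 7% at .02, 11–12% at .05 and 17–18% at .10. Clinic adjustment therefore does not remove the effect.

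**If controls share the CHW effect.** Suppose controls are spread over the same CHWs and carry a fraction s of the effect. With total variance 1 in each arm, the true variance of the contrast is (1 − s)² × ICC/6 + [(1 − ICC) + (1 − s² × ICC)]/135, against 2/135 in the model. At ICC .05:
- s = 0: (.00833 + .01444)/.01481 = 1.5375; type I error 11.4%.
- s = .5: (.00208 + .01435)/.01481 = 1.109; r = 1.053; type I error 6.3% (simulated 6–7%).
- s = 1: (0 + .01407)/.01481 = .95; r = .975; type I error 4.4% (simulated 4–5%).

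**Cost of modelling CHW.** With the CHW variance treated as known, nominal .80 power becomes Φ(2.80/r − 1.96). For N = 270 and 6 CHWs this is .76, .72, .62 and .49 at ICC .01, .02, .05 and .10. The variance must in fact be estimated. With two CHWs in each of three clinics, the within-clinic CHW variance has 3 × (2 − 1) = 3 degrees of freedom. In simulation a partially nested analysis with Satterthwaite degrees of freedom kept type I error at about 5–6%, but nominal 80% power fell to about 72% even at ICC 0.

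**The case against.** Several points against a stronger reading stand.

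- A reader might infer that the trial's false-positive rate is above 5%. The documents do not support that without a condition: they give no CHW ICC, and at zero the rate is 5%. Six CHWs is also the stated minimum, and with 12 the inflation is clearly smaller.
- A reader might infer that each YMHP participant has one CHW throughout. The protocol never says so, describes no assignment of participants to CHWs, and allows for turnover. Shared delivery weakens clustering by CHW.
- A reader might infer that controls have no CHW contact. Protocol 6.0 gives them one meeting with PrEP referral, and PrEP uptake is one of the outcomes. Whatever CHW effect is common to both arms cancels. One meeting against four motivational-interviewing sessions makes full cancellation unlikely, but partial cancellation is plausible.
- Fidelity coding and supervision of individual CHWs might be read as proof that outcomes differ by CHW. They show that the protocol allows for uneven delivery and tries to reduce it. They say nothing about the ICC of STIs, condomless sex or PrEP uptake.
- The simulation is a cross-sectional linear model. The SAP plans longitudinal growth mixture models, partly for binary and count outcomes, so the percentages do not transfer.
- The SAP's model paragraph names clinic-based versus remote delivery, where CHWs deliver both sides and the one-arm argument does not apply. But the primary hypothesis in the same section is YMHP versus standard of care, the later text regresses on intervention condition, and clinic is the only clustering level given anywhere.

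None of this removes the omission. It limits what can be claimed about its size, and it counts against making a CHW model the primary analysis.

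**Conclusion.** The point holds conditionally. If CHWs differ in their effect on YMHP participants beyond what they share with controls, the standard errors for YMHP versus standard of care are too small, and the clinic level does not repair them. The argument also supposes inference to CHWs in general, which fits the trial's scalability aims.

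The size is uncertain: from negligible (ICC near 0, many CHWs, or a largely shared effect) to a type I error of about 17% for a nominal 5% test (N = 270, 6 CHWs, ICC .10, nothing shared). The ICC range, 1:1 allocation, the count of 12 CHWs and the linear model are assumptions.

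The further step, that the primary model must be replaced, is not supported. With six CHWs the replacement would lose power even if CHWs did not differ at all. This is an inexpensive safeguard worth adding before the analysis.

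**What to change.** **SAP 1.2.** Prespecify a sensitivity analysis of YMHP versus standard of care, based on the SAP's direct model in which intervention condition predicts the growth factors, and run it whether or not latent classes are found.
- Add a CHW effect in the YMHP arm only and keep the clinic adjustment.
- Use a small-sample correction suited to the outcome type. Satterthwaite and Kenward-Roger apply to linear models only, so name another method for binary and count outcomes.
- Define a participant's CHW as the one who delivered most of that participant's sessions. Where sessions are shared, this is an approximation.
- Treat YMHP participants with no session as singleton clusters. The protocol lets those who decline recording or sessions stay in follow-up.
- Report the estimated CHW variance with its uncertainty, and say whether the conclusion changes.

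**SAP 1.2.1.** Next to the clinic argument, give the design effect for a range of CHW ICCs and CHW counts, at the sample size that applies once 270 and 180 are reconciled.

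**Data.** Confirm that the Clinical Session Form records which CHW delivered the session. The protocol says who submits the form, not which fields it holds.

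**Cost.** SAP wording and modest programming; no new data collection if the form already identifies the CHW. With few CHWs the intervals will be wide and the CHW variance imprecise, so a changed conclusion in this analysis should be read as reduced certainty, not as evidence of no effect.
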